### 6.2.2 Appropriateness of a Linear Model

To assess the appropriateness of a linear model, normal Q-Q plots for the standardized residuals and the random effects, and plots of standardized residuals versus concentration, fitted values, centered baseline QTcF, nominal time, and active treatment will be produced. Scatter plots for standard residuals versus continuous covariates and box plots for standard residuals versus discrete covariates will be provided. The scatter plots of standardized residuals versus concentration, and centered baseline QTcF by LOESS fitting (i.e., locally weighted scatter plot smoothing (as described by Cleveland) will also be produced with optimal smoothing parameters selected by the Akaike information criterion with a correction. A scatter plot of observed concentration and  $\Delta$ QTcF with a LOESS smooth line with 90% CI and a linear regression line will also be provided to check the assumption of a linear concentration-QTc relationship. If there is an indication that a linear model is inappropriate, additional models will be fitted, in particular an  $E_{max}$  model. The concentration-QTc analysis will then be repeated for the model found to best accommodate the nonlinearity detected.

## 6.3 Assay Sensitivity

The analysis to show assay sensitivity will be based on the concentration-QTc analysis of the effect on  $\Delta$ QTcF of [CC1] mg oral moxifloxacin using a similar model as for the primary analysis. That is, the relationship between moxifloxacin plasma concentration and  $\Delta$ QTcF will be investigated by linear mixed-effects modeling. The model will include  $\Delta$ QTcF as the dependent variable, moxifloxacin plasma concentration as the explanatory variate (0 for placebo), centered baseline QTcF as an additional covariate, study treatment (moxifloxacin = 1 or placebo = 0), and time (i.e., post-dose time point) as categorical factors, and a random intercept and slope per subject (Garnett et al). The geometric mean of the individual  $C_{max}$  values for subjects receiving the single dose of [CC1] mg moxifloxacin will be determined. The predicted effect and its 2-sided 90% CI for  $\Delta\Delta$ QTcF (i.e., slope estimate  $\times$  concentration + treatment effect-specific intercept) at this geometric mean  $C_{max}$  will be obtained.

If the slope of the moxifloxacin plasma concentration/ $\Delta$ QTcF relationship is statistically significant at the 10% level in a 2-sided test and the lower bound of the 2-sided 90% CI of the predicted QT effect at the observed geometric  $C_{max}$  of the [CC1] mg dose is above 5 ms, assay sensitivity will be deemed to have been demonstrated.

## 6.4 Categorical Analysis

Results for categorical outliers, T-wave morphology, and U-wave presence will be summarized in frequency tables with counts and percentages for both number of subjects and number of time points.

A subject or time point will be determined as an outlier if the following criteria (which are assessed separately) are met for the ECG intervals (Table 2). Each subject meeting a categorical threshold will be counted once, using the largest value.

**Table 2 Criteria for determining a subject or time point outlier**

ECG interval	Categorical outlier criteria
QTcF	Treatment-emergent value of $> 450$ and $\leq 480$ ms when not present at baseline (new onset)
	Treatment-emergent value of $> 480$ and $\leq 500$ ms when not present at baseline (new onset)
	Treatment-emergent value of $> 500$ ms when not present at baseline (new onset)
	Increase of QTcF from baseline of $> 30$ and $\leq 60$ ms
	Increase of QTcF from baseline $> 60$ ms
PR	Increase of PR from baseline $> 25\%$ resulting in PR $> 200$ ms
QRS	Increase of QRS from baseline $> 25\%$ resulting in QRS $> 120$ ms
HR	Decrease of HR from baseline $> 25\%$ resulting in HR $< 50$ bpm
	Increase of HR from baseline $> 25\%$ resulting in HR $> 100$ bpm

All outliers will be summarized for each treatment on the basis of incidence rates. A subject will be counted only once for a particular outlier event if the subject experiences more than 1 episode of that event. The total number of time points will be based on the number of observed time points across all subjects within a treatment group.

For T-wave morphology and U-wave presence, treatment-emergent changes will be assessed, i.e., changes not present at baseline. For each category of T-wave morphology and of U-waves, the category will be deemed as present if observed in all replicates at the time point. For baseline, the category will be deemed as present if observed in any replicates from all time points that constitute baseline, i.e., the 3 time points prior to dosing on Day 1 in each period.

The T-wave morphology and U-wave presence categories are described as follows (Table 3).

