**Table 3 T-wave morphology and U-wave presence categories (assessed manually)**

Category	Description
Normal T-wave (+)	Any positive T-wave not meeting any criterion below.
Flat T-wave	T-amplitude $< 1$ mm (either positive or negative), including flat isoelectric line.
Notched T-wave (+)	Presence of notch(es) of at least 0.05 mV amplitude on ascending or descending arm of the positive T-wave.
Biphasic	T-wave that contains a second component with an opposite phase that is at least 0.1 mV deep (both positive/negative and negative/positive and polyphasic T-waves included).

Category	Description
Normal T-wave (-)	T-amplitude is negative, without biphasic T-wave or notches.
Notched T-wave (-)	Presence of notch(es) of at least 0.05 mV amplitude on descending or ascending arm of the negative T-wave.
U-waves	Presence of abnormal U-waves.

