## Appendix A: Expert Precision QT Analysis

Expert Precision QT analysis (formerly High Precision QT analysis) will be performed on all analyzable (non-artifact) beats in the 10 ECG replicates (1 replicate consists of one 14 second ECG). Statistical quality control procedures will be used to review and assess all beats and identify “high” and “low” confidence beats using several criteria including:

- QT or QTc values exceeding or below certain thresholds (biologically unlikely)
- RR values exceeding or below certain thresholds (biologically unlikely)
- Rapid changes in QT, QTc, or RR from beat to beat

Placement of fiducials and measurements of all primary ECG parameters (QT, QTc, RR) in all recorded beats of all replicates will be performed using the iCOMPAS software. All beats that are deemed “high confidence” will not be reviewed by an ERT ECG analyst. All low confidence beats will be reviewed manually by an ERT ECG analyst and adjudicated using pass-fail criteria. The beats found acceptable by manual review will be included in the analysis. The beats confirmed to meet fail criteria will not be included in the analysis.

For the purpose of measuring PR and QRS intervals and to assess T-wave morphology and presence of U-waves, the TQT Plus algorithm will select the 3 ECG replicates with the highest quality score from the ECG extraction window. These 3 ECGs will be analyzed using a semi-automated process to determine these parameters. If 3 consecutive usable beats cannot be identified in at least 2 of the 3 replicates, then all beats in all replicates will be reviewed for that time point using a manual analysis.

If manual analysis is required, then all beats in a minimum of 3 replicates will be reviewed using the iCOMPAS software. The ERT ECG analyst will review all usable beats in Lead II (or an alternate lead) for each replicate and will review and/or adjust the fiducial placements (onset of P, onset of Q, offset of S, and offset of T-wave that were electronically marked) of each waveform and also document the T-wave morphology and the presence of U-waves for each beat. A replicate will only be reported if it has 3 approved, usable beats.

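### Does the all-replicates rule for T-wave and U-wave findings fail because its replicate set and two of its categories are not fully pinned down?

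*SAP*

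**What the plan says.** Morphology is a secondary cardiodynamic endpoint (ECG SAP 4.2.2). Section 6.4 summarises it as counts and percentages of subjects and of time points, in Table 14.2.3.1.8. Only changes absent at baseline count. After dosing, "the category will be deemed as present if observed in all replicates at the time point". At baseline, a sighting in any replicate from the three pre-dose time points is enough.

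Appendix A supplies the replicates. By default the software takes the three with the best quality score out of up to 10 extracted (Section 5.4), and "These 3 ECGs will be analyzed using a semi-automated process to determine these parameters". If fewer than two of those three yield three consecutive usable beats, "then all beats in all replicates will be reviewed for that time point using a manual analysis". The next paragraph says that when manual analysis is needed, "then all beats in a minimum of 3 replicates will be reviewed using the iCOMPAS software". There the analyst must "also document the T-wave morphology and the presence of U-waves for each beat", and a replicate is reported only if three of its beats are accepted as usable.

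Table 3 defines the categories. Flat is an amplitude below 1 "mm (either positive or negative), including flat isoelectric line". Normal (-) reads "T-amplitude is negative, without biphasic T-wave or notches". Normal (+) is the only category that expressly excludes T-waves meeting another definition.

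**The concern.** A rule that needs agreement across every replicate becomes stricter as replicates are added, so it should rest on a known set. At a manual-review time point the text could be taken to mean anything from three to 10. On the default route, two of the three selected replicates are enough to avoid manual review. No rule turns beat-level findings into a replicate result, and the title of Table 3 says the categories are assessed manually while Appendix A calls the default process semi-automated.

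The overlap affects every time point, not only those sent to manual review. If the reader must choose one label and codes the three replicates Flat, Flat and Normal (-), neither category is seen in all of them and a new abnormality drops out of the table. The baseline sentence could also be read as requiring a sighting at each of the three pre-dose time points, which would make treatment-emergent calls far easier to reach. At stake are the counts for a named secondary endpoint.

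**Working it through.** The plan states no figure for this endpoint, so there is none to reproduce. The check compares the texts and then sizes the consequence. Per-replicate rates are assumptions throughout.

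**1. Replicate set.** Reviewing all replicates satisfies a minimum of three, so the two Appendix A sentences can both hold, the second acting as a floor. The default route is fixed at three. On the manual route, the reporting condition gives a natural meaning to the rule in 6.4: all *reported* replicates.

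With per-replicate presence p, P(all of k) = p^k if replicates are independent. With correlation ρ, use a beta-binomial with a + b = 1/ρ − 1 and a = p(a + b):

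P(all of k) = ∏ (a + i)/(a + b + i), for i = 0 to k − 1.

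Example: p = 0.8, ρ = 0.5, k = 3 gives 0.8 × 1.8/2 × 2.8/3 = 0.672.

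| p | k | ρ = 0 | ρ = 0.5 | ρ = 0.7 |
|---|---|---|---|---|
| 0.8 | 3 | 0.512 | 0.672 | 0.725 |
| 0.8 | 10 | 0.107 | 0.538 | 0.653 |
| 0.9 | 3 | 0.729 | 0.827 | 0.858 |
| 0.9 | 10 | 0.349 | 0.740 | 0.814 |

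The large gap, 0.729 against 0.349, needs independent replicates and 10 reportable replicates at a time point where at most one of the best three had three consecutive usable beats. Manual review does not require consecutive beats, so this is possible but extreme. With ρ = 0.7 and p = 0.9 the gap is 0.858 − 0.814 = 0.044. For two replicates instead of three on the default route, the independent figures at p = 0.9 are 0.81 and 0.729.

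**2. Category overlap.** Take a smooth negative T-wave shallower than 1 mm in all three replicates.

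- *Scored category by category, as 6.4 is written.* It meets Flat in all three and Normal (-) in all three. Both are counted, and P(neither) = 0.
- *Forced single label*, Flat with probability f in each replicate: P(neither) = 1 − P(all Flat) − P(all Normal (-)). At f = 0.8 and ρ = 0 this is 1 − 0.512 − 0.008 = 0.480. At ρ = 0.5, P(all Normal (-)) = 0.2 × 1.2/2 × 2.2/3 = 0.088, so 1 − 0.672 − 0.088 = 0.240. At ρ = 0.7 it is 0.144. At f = 0.9 the three values are 0.270, 0.135 and 0.081; at f = 0.5 they are 0.750, 0.375 and 0.225.
- *Any convention applied consistently to such a T-wave.* f is 0 or 1, and P(neither) = 0.

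Making the two categories exclusive would not remove the split. For a T-wave close to 1 mm deep, let f be the chance that a replicate measures below 1 mm. Under exclusive categories the same formula applies, 0.750 at f = 0.5 and ρ = 0. Under the overlapping definitions, that T-wave is Normal (-) in every replicate and is counted.

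**3. Baseline.** The sentence identifies the set as the three pre-dose time points, and pooling them is the natural reading. For scale, assume a stable 30% rate with no drug effect, three independent replicates and the 12 post-dose time points of Section 4. The chance of at least one post-dose call is 1 − (1 − 0.3³)^12 = 0.280. Pooled baseline: 0.7⁹ × 0.280 = 0.011. One sighting required at each time point: [1 − (1 − 0.7³)³] × 0.280 = 0.716 × 0.280 = 0.201. The contrast matters only if the strained reading is adopted.

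**4. Who decides.** Section 4 has the core laboratory measure the ECGs blind and locks the ECG database before any statistical analysis. Replicate selection, the step from beats to a replicate label, and Flat against Normal (-) are settled by readers who do not know the treatment. They are not left to whoever programs the table.

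**The case for a change.** The best case for a change is that the ECG SAP sets out in its Introduction to give full details of analyses and derivations, that morphology is a named secondary endpoint, and that a few words would close the overlap. An ambiguity shared by all treatments does not make the counts reproducible, and missed calls would lower them in every arm. The overlap also arises on the default route, so it cannot be dismissed as rare.

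Part of this stands. Table 3 does let one T-wave meet two definitions with no precedence. Appendix A does not say in terms which replicates the rule uses after manual review, and the step from beat to replicate is unwritten. The rest is thin. A semi-automated process can include a human reader, and that phrase covers PR, QRS and morphology together. A stop-at-three procedure or a majority-of-beats rule would be new reading or derivation rules, not clarifications. If fewer than three replicates were reportable, the set would still vary.

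**Conclusion.** No change is needed. The definitional overlap is genuine but amounts to missing detail that the core laboratory fills under blinding. At worst, a smooth negative T-wave shallower than 1 mm appears in two rows of Table 14.2.3.1.8, or in one row under the laboratory's own convention, with the same rule in every arm. Listing 16.2.6.4 shows the underlying findings. The replicate wording concerns only manual-review time points, for which the documents give no frequency, and it has a workable reading: all reported replicates.

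The large percentages depend on assumptions that the documents do not support: independent replicates, inconsistent forced coding, 10 reportable replicates at a time point that failed the quality check, or an unnatural reading of the baseline sentence. The table is descriptive and carries no decision rule. Neither the primary concentration-QTc analysis nor the assay-sensitivity test uses morphology, so no conclusion of the trial turns on this point.

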**Table 3 T-wave morphology and U-wave presence categories (assessed manually)**

Category	Description
Normal T-wave (+)	Any positive T-wave not meeting any criterion below.
Flat T-wave	T-amplitude $< 1$ mm (either positive or negative), including flat isoelectric line.
Notched T-wave (+)	Presence of notch(es) of at least 0.05 mV amplitude on ascending or descending arm of the positive T-wave.
Biphasic	T-wave that contains a second component with an opposite phase that is at least 0.1 mV deep (both positive/negative and negative/positive and polyphasic T-waves included).

Category	Description
Normal T-wave (-)	T-amplitude is negative, without biphasic T-wave or notches.
Notched T-wave (-)	Presence of notch(es) of at least 0.05 mV amplitude on descending or ascending arm of the negative T-wave.
U-waves	Presence of abnormal U-waves.

## 6.5 By-Time Point Analysis

The “by time point analysis” will be based on cardiodynamic population. The “by time point analysis” for QTcF will be based on a mixed-effect repeated measures model with  $\Delta$ QTcF as the dependent variable; period, time (i.e., post-dose time point: categorical), treatment (therapeutic dose of LOXO-292, supratherapeutic dose of LOXO-292, moxifloxacin, and placebo), and time-by-treatment interaction as fixed effects; and baseline QTcF as a covariate. An unstructured covariance matrix will be specified for the repeated measures at post-dose time points for subject within treatment period. If the model with an unstructured covariance matrix fails to converge, other covariance matrices such as compound symmetry and autoregressive will be considered. The model will also include a subject-specific random effect. If the fixed effect for period should prove to be not significant (i.e., if the  $P$  value  $> 0.1$ ), the fixed effect may be removed from the model and the analysis will be repeated without period. From this analysis, the LS mean and 2-sided 90% CI will be calculated for the contrast “LOXO-292 versus placebo” at each dose of LOXO-292 and each post-dose time point, separately. If a carry-over effect is observed (Section 6.1), the period-by-treatment interaction and the period-by-treatment-by-time interaction will also be included in the model.

For HR, PR, and QRS intervals, the analysis will be based on the post-dose  $\Delta$ HR,  $\Delta$ PR, and  $\Delta$ QRS. The same (by-time point analysis) model will be used as described for QTcF. The LS mean, SE, and 2-sided 90% CI from the statistical modeling for both change-from-baseline and placebo-corrected change-from-baseline values will be listed in the tables and graphically displayed.

The SAS code for the by-time point analysis for QTcF is as follows:

```

PROC MIXED DATA=ECG;
CLASS SUBJID TREAT TIME PERIOD SEQUENCE;
MODEL DQTC=BASE TREAT TIME TREAT*TIME PERIOD SEQUENCE/DDFM=KR;
random intercept / SUBJECT =SUBJID type=UN;
REPEATED TIME / SUBJECT = SUBJID*PERIOD type = un;
LSMEANS TREAT*TIME/CL DIFF ALPHA=0.1;
RUN;

```

Where ECG=Cardiodynamic population, SUBJID=subject identifier, TREAT=treatment (therapeutic dose of LOXO-292, supratherapeutic dose of LOXO-292, moxifloxacin, and placebo), TIME=nominal time point, BASE= baseline QTcF, PERIOD=period, SEQUENCE=sequence, and DQTC= $\Delta$ QTcF.

## 6.6 Determination of Sample Size

The sample size determination is based on testing to support a non-inferiority hypothesis, with a non-inferiority margin of 10 ms for this determination. Using non-inferiority margin of 10 ms, assuming a 1-sided 0.05 significance level and a common within-subject SD of 8 ms for QTc, a sample size of 30 evaluable subjects (allowing for 2 dropouts) would be expected to provide at least ~~80~~% power to detect an expected mean difference of 3 ms in  $\Delta$ QTc between LOXO-292 and placebo.

The proposed 4-way crossover design in this study, using 32 subjects randomized to 1 of 4 treatment sequences will result in up to 32 sets of observations each for moxifloxacin and placebo. Given what was reported in the literature, this sample size is deemed appropriate to detect a drug-induced QTc prolongation by moxifloxacin of greater than 5 ms.

## 8 Tables, Figures, and Listings

### 8.1 Tables

Number	Title	Comments
14.2.3.1.1	Baseline values of ECG parameters with descriptive statistics	Number of subjects (n), mean, SD, SE, 90% CI, median, minimum, and maximum from descriptive analysis will be given by treatment for each ECG parameter.
14.2.3.1.2	Absolute values of ECG parameters with descriptive statistics	n, mean, SD, SE, 90% CI, median, minimum, and maximum from descriptive statistics will be given by treatment and post-dose time point for each ECG parameter.
14.2.3.1.3.1- 14.2.3.1.3.2	Change-from-baseline QTcF, HR, PR, and QRS ( $\Delta$ QTcF, $\Delta$ HR, $\Delta$ PR, and $\Delta$ QRS) at each time point	n, LS mean, SE, and 90% CI from the statistical modeling will be given by treatment and time point (Section 6.5).
14.2.3.1.4.1- 14.2.3.1.4.4	Placebo-corrected change-from-baseline QTcF, HR, PR, and QRS ( $\Delta\Delta$ QTcF, $\Delta\Delta$ HR, $\Delta\Delta$ PR, and $\Delta\Delta$ QRS) at each time point	LS mean, SE, and 90% CI from the statistical modeling will be given by treatment and time point (Section 6.5).
14.2.3.1.5	QTcF outliers per absolute category across treatment groups	Number (%) of subjects and time points with QTcF $> 450$ and $\leq 480$ ms, $> 480$ and $\leq 500$ ms, and $> 500$ ms by treatment (Section 6.4).
14.2.3.1.6	QTcF outliers per change-from-baseline category across treatment groups	Number (%) of subjects and time points with $\Delta$ QTcF $> 30$ and $\leq 60$ ms, and $> 60$ ms by treatment (Section 6.4).

Number	Title	Comments
14.2.3.1.7	Categorical analysis for HR, PR, and QRS groups	Number (%) of subjects and time points with $\Delta\text{PR} > 25\%$ and $\text{PR} > 200 \text{ ms}$ at post-baseline; $\Delta\text{QRS} > 25\%$ and $\text{QRS} > 120 \text{ ms}$ at post-baseline; HR decrease from baseline $> 25\%$ and $\text{HR} < 50 \text{ bpm}$ at post-baseline; and HR increase from baseline $> 25\%$ and $\text{HR} > 100 \text{ bpm}$ at post-baseline (Section 6.4).
14.2.3.1.8	T-wave morphology and U-wave presence across treatment: treatment-emergent changes across treatment groups	Number (%) of subjects and time points falling into each of T-wave categories: Normal (+), Flat, Notched (+), Biphasic, Normal (-), Notched (-) as defined in Section 6.4.
14.2.3.1.9.1	Concentration-QTc analysis of LOXO-292 and associated $\Delta\text{QTcF}$ prolongation	Fixed-effect estimations and corresponding $P$ values will be given (Section 6.2).
14.2.3.1.9.2	Assay sensitivity analysis of moxifloxacin and associated $\Delta\text{QTcF}$ prolongation	Fixed-effect estimations and corresponding $P$ values will be given (Section 6.3).
14.2.3.1.10.1	Predicted $\Delta\Delta\text{QTcF}$ interval at geometric mean peak LOXO-292 concentration	Section 6.2.
14.2.3.1.10.2	Predicted $\Delta\Delta\text{QTcF}$ interval at geometric mean peak moxifloxacin concentration	Section 6.3.

## 8.2 Figures

Number	Title	Comments
14.2.3.2.1	Absolute QTcF across time points	Mean and 90% CI from descriptive analysis will be given by treatment.
14.2.3.2.2.1- 14.2.3.2.2.4	Change-from-baseline QTcF, HR, PR, and QRS ( $\Delta\text{QTcF}$ , $\Delta\text{HR}$ , $\Delta\text{PR}$ , and $\Delta\text{QRS}$ ) across time points	LS mean and 90% CI from the statistical modeling will be shown by treatment for each parameter (Section 6.5).
14.2.3.2.3.1- 14.2.3.2.3.4	Placebo-corrected change-from-baseline QTcF, HR, PR, and QRS ( $\Delta\Delta\text{QTcF}$ , $\Delta\Delta\text{HR}$ , $\Delta\Delta\text{PR}$ , and $\Delta\Delta\text{QRS}$ ) across time points	LS mean and 90% CI from the statistical modeling will be shown by treatment (Section 6.5).
14.2.3.2.4.1	Scatter plot of QTcF versus RR by treatment	Scatter plots of QTcF and RR intervals by treatment with regression lines will be given (Section 6.2).
14.2.3.2.4.2	QTcF-RR quantile plot by treatment	QTcF-RR quantile plots (with quantiles) with linear mixed-effects line and 90% CI will be given (Section 6.2).
14.2.3.2.5.1	Plot of mean LOXO-292 plasma concentrations over time	Section 6.2.

Number	Title	Comments
14.2.3.2.5.2	Plot of mean moxifloxacin plasma concentrations over time	Section 6.3.
14.2.3.2.6	Joint plot of LOXO-292 plasma concentrations and $\Delta\Delta QTcF$ over time	Section 6.2.1.
14.2.3.2.7	Hysteresis plot of LOXO-292 plasma concentration and $\Delta\Delta QTcF$ connected in temporal order	This is what is often called a “Hysteresis plot” (Section 6.2.1).
14.2.3.2.8.1	Scatter plot of observed LOXO-292 plasma concentrations and $\Delta QTcF$ by subject	Scatter plot of $\Delta QTcF$ versus concentration with LOESS line and 90% CI and simple linear regression line (Section 6.2).
14.2.3.2.8.2	Scatter plot of observed LOXO-292 plasma concentrations and estimated placebo-adjusted $\Delta QTcF$ by subject	Scatter plot of estimated placebo-adjusted $\Delta QTcF$ versus observed concentration and linear mixed-effect regression line with CI (Section 6.2).
14.2.3.2.8.3	Scatter plot of observed moxifloxacin plasma concentrations and $\Delta QTcF$ by subject	Scatter plot of $\Delta QTcF$ versus concentration with LOESS line and 90% CI and simple linear regression line (Section 6.3).
14.2.3.2.8.4	Scatter plot of observed moxifloxacin plasma concentrations and estimated placebo-adjusted $\Delta QTcF$ by subject	Scatter plot of estimated placebo-adjusted $\Delta QTcF$ versus concentration and linear mixed-effect regression line with CI (Section 6.3).
14.2.3.2.9.1	Model-predicted $\Delta\Delta QTcF$ (mean and 90% CI) and estimated placebo-adjusted $\Delta QTcF$ (mean and 90% CI) across deciles of LOXO-292 plasma concentrations	Section 6.2.
14.2.3.2.9.2	Model-predicted $\Delta\Delta QTcF$ (mean and 90% CI) and estimated placebo-adjusted $\Delta QTcF$ (mean and 90% CI) across deciles of moxifloxacin plasma concentrations	Section 6.3.
14.2.3.2.10.1	Predicted $\Delta\Delta QTcF$ interval at geometric mean peak LOXO-292 concentrations	Section 6.2.
14.2.3.2.10.2	Predicted $\Delta\Delta QTcF$ interval at geometric mean peak moxifloxacin concentrations	Section 6.3.
14.2.3.2.11.1	Scatter plot of standardized residuals versus fitted values for LOXO-292	Section 6.2.2.
14.2.3.2.11.2	Scatter plot of standardized residuals versus fitted values for moxifloxacin	Section 6.3.

Number	Title	Comments
14.2.3.2.12.1	Scatter plot of standardized residuals versus LOXO-292 concentrations with LOESS	Section 6.2.2.
14.2.3.2.12.2	Scatter plot of standardized residuals versus moxifloxacin concentrations with LOESS	Section 6.3.
14.2.3.2.13.1	Scatter plot of standardized residuals versus centered baseline QTcF with LOESS for LOXO-292	Section 6.2.2.
14.2.3.2.13.2	Scatter plot of standardized residuals versus centered baseline QTcF with LOESS for moxifloxacin	Section 6.3.
14.2.3.2.14.1	Box plot of standardized residuals versus nominal time for LOXO-292	Section 6.2.2.
14.2.3.2.14.2	Box plot of standardized residuals versus nominal time for moxifloxacin	Section 6.3.
14.2.3.2.15.1	Box plot of standardized residuals versus treatment for LOXO-292	Section 6.2.2.
14.2.3.2.15.2	Box plot of standardized residuals versus treatment for moxifloxacin	Section 6.3.
14.2.3.2.16.1	Normal Q-Q plot of standardized residuals for LOXO-292	Section 6.2.2.
14.2.3.2.16.2	Normal Q-Q plot of standardized residuals for moxifloxacin	Section 6.3.
14.2.3.2.17.1	Normal Q-Q plots of the estimated random effects for LOXO-292	Section 6.2.2.
14.2.3.2.17.2	Normal Q-Q plots of the estimated random effects for moxifloxacin	Section 6.3.

